B. Study Type and Design: Type of Study: multi-center prospective randomized controlled trial. Study Design: We will initially monitor 4 groups of patients. The first group (20 patients) will undergo bony tumor resection of the femur or proximal tibia and endoprosthetic reconstruction with TXA. The second group (20 patients) will undergo bony tumor resection of the femur or proximal tibia and endoprosthetic reconstruction without TXA. The third group (50 patients) will undergo soft tissue sarcoma resection of the lower extremity with TXA. The fourth group (50 patients) will undergo soft tissue sarcoma resection of the lower extremity without TXA. The use of TXA is well established for arthroplasty at this institution given the body of evidence supporting both efficacy and safety. Treatment assignments will be stratified by type of resection location. Patient randomization will be done via randomization program through REDCap. The randomization process will be performed centrally at Kansas University Medical Center and the treating surgeon will not have access to the randomization list. Randomization will occur prior to definitive surgical procedure, and the treating surgeon and pharmacy will be notified to ensure adequate vials of tranexamic acid are available in the operating room (investigators/surgeons are not blinded). Patients will be blinded to treatment allocation. Those in groups using TXA will receive 1g TXA IVPB 10 minutes prior to incision and a second dose of 1g IVPB at the time of closure which is the standard protocol used for total joint arthroplasty. The TXA will be administered by the anesthesia team. If the surgeon determines intraoperatively that TXA is required for patient safety, the drug should be used. Patients receiving a non-standard dosing of TXA will then be excluded from the study. Routine hemoglobin and hematocrit measurements will be observed preoperatively as well as postoperatively at 6 hours and in the mornings of postoperative days 1-3. This laboratory regimen is currently the standard of care and utilized routinely. Patients may be discharged prior to obtaining all 4 blood draws. If a patient is discharged prior to postoperative day 3, no additional blood draw will be performed. Additionally, both intraoperative and postoperative incidents of blood transfusion will be monitored to calculate transfusion rates. Postoperative erythrocyte transfusions will be given for hemoglobin below 7.0 as is the current practice guidelines used by the attending surgeons at this institution. Other facilities are encouraged to follow this protocol, however, the ultimate decision for blood transfusion will be at the discretion of the treating physician. Surgical drains are also used routinely and their daily output will be recorded until they are deemed appropriate to pull by the attending surgeon. Patients will be clinically monitored daily while in the hospital and in subsequent follow up visits for symptoms of DVT or embolism and appropriate diagnostic screening with venous Doppler will be utilized if symptoms are present, as is also part of current routine postoperative care. Our DVT prophylaxis protocol postoperatively will be 4 weeks of aspirin 81 mg BID unless medical co-morbidities necessitate the use of other anti-coagulation. Mechanical DVT prophylaxis in the form of sequential compression devices will also be

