
utilized. We also plan to record patient specific factors including age, sex, smoking status, BMI, pre-op diagnosis, operative time, comorbidities, and length of stay. These variables will be analyzed independently to detect any correlation with perioperative blood loss and erythrocyte transfusion rate.

C. Sample size, statistical methods, and power calculation

Method of Randomization: Patient randomization will be done via a randomization program through REDCap. The randomization process will be performed centrally at Kansas University Medical Center and the treating surgeon will not have access to the randomization list. Randomization will occur prior to definitive surgical procedure, and the treating surgeon and pharmacy will be notified to ensure adequate vials of tranexamic acid are available in the operating room (investigators/surgeons are not blinded). Patients will be blinded to treatment allocation. Treatment assignments will be stratified by type of resection. A power of 0.9 would require a total of 40 patients (20 per treatment group) be enrolled in the bony tumor group and 100 patients (50 per treatment group) in the soft tissue tumor group.

Since we are gathering entirely objective data the treating surgeon does not need to be blinded. Group differences in preoperative hemoglobin and hematocrit, transfusion requirements, drain output at 24 hours, and changes in hemoglobin and hematocrit will be compared using pairwise Student T-test analysis. Pairwise T-tests between each of the groups (for continuous variables) and Chi squared analysis (for categorical variables) will be used to determine if a statistically significant difference exists between the groups in terms of the patient specific factors that are also collected and analyzed (age, sex, smoking status, BMI, operative time, length of stay).

D. Subject Criteria (See Vulnerable Populations appendix, if applicable):

Inclusion criteria: Patients (male or female) between the ages of 18-90 undergoing wide resection of a malignant bony tumor of the lower extremity with endoprosthetic reconstruction or resection of soft tissue sarcoma measuring >5cm.

Exclusion criteria:

- Patients undergoing revision endoprosthetic reconstruction
- Patients with known coagulopathy
- Known history of DVT or embolic disease
- Benign tumors
- Patients with allergy to TXA
- Those refusing blood products
- Those concurrently on anti-coagulant therapy
- Pregnant and nursing women

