G. Location where study will be performed: This will be a multi-institutional study with the University of Kansas Medical Center being the coordinating site. We have interest from multiple institutions but they are awaiting our IRB approval. These include the University of Chicago, Oklahoma, St. Louis University, Cleveland Clinic, and MUSC, Iowa, Penn, and others. Recruitment of study participants will take place at the University of Kansas Medical Center and the University of Kansas Hospital Indian Creek Campus. Recruitment will also take place at participating institutions. Data will be collected for the primary and secondary endpoints from patients' electronic medical records and will be compiled electronically. The research subject's records will be stored electronically on a hard-drive in a passwordprotected and encrypted computer at the University of Kansas Medical Center **H. Collaboration (with another institution, if applicable):** see Item "I" below.

I. Single IRB Review for a Multi-site study (if applicable):

1. For which sites will KUMC serve as the IRB of record? Only Kanas University Medical Center. Participating institutions will work through their own IRBs for review and approval.
2. Indicate which study activities will occur at each site. If all study procedures will be identical across study sites, state this. Identical across sites.
3. Describe how you will assess the capacity of each site to perform the research (e.g., expertise, staffing, space, equipment, etc.) If applicable, include site evaluation tools in your IRB submission. All sites will have a fellowship trained orthopaedic oncologist who treats sarcomas regularly. They will all be at academic institutions with their own IRBs and experience in conducting clinical trials.

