1. Describe steps to be taken to assure that the data collected are accurate, consistent, complete and reliable. (source data verification, audits or self – assessment) Source data verification and self-audits will be performed. The protocol for the clinical trial will be spelled out for the participants. A discussion will be had between the PI at KUMC and the PI at the participating institution to ensure the protocol is understood.

V. Data Analysis and Reporting

A. Statistical and Data Analysis: Group differences in preoperative hemoglobin and hematocrit, transfusion requirements, drain output at 24 hours, difference in hemoglobin balance method, and changes in hemoglobin and hematocrit will be compared using pairwise Student T-test analysis. Pairwise T-tests between each of the groups (for continuous

variables) and Chi squared analysis (for categorical variables) will be used to determine if a statistically significant difference exists between the groups in terms of the patient specific factors that are also collected and analyzed (age, sex, smoking status, BMI, operative time, length of stay, presence of coagulopathy, specific anticoagulation regimen should it differ from study protocol, size of resection, depth of resection, location of tumor, pathologic diagnosis, stage of disease).

B. Outcome: We expect the results to be similar to the TXA arthroplasty studies/literature with regards to decreased perioperative blood loss and decreased transfusion rates. There are not necessarily any criteria for success or failure. The results of this study will help provide a definitive answer regarding the safety and efficacy of TXA in oncologic patients. This will help unify the musculoskeletal oncology field in their use or abandonment of TXA.

C. Study results to participants: The study results/conclusions will not be given to subjects unless they are specifically asked for at future scheduled outpatient clinic visits. Once the proposed study is completed a conversation with subjects can occur on an outpatient basis at their routine scheduled clinic visits regarding our results and conclusions if desired. The subjects reserve the right to know what conclusions were drawn from the study they directly participated in. In addition, we plan to publish a manuscript with our results/conclusions after completion of the study which can be sought after if desired.

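### Transfusion practice may differ by site, and the unadjusted arm comparisons leave that variation in: a cheap precision gain, not a bias

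*Combined protocol and SAP*

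**What the plan says.** Section II.B ties postoperative transfusion to local practice: "Postoperative erythrocyte transfusions will be given for hemoglobin below 7.0 as is the current practice guidelines used by the attending surgeons at this institution". The next sentence covers the other hospitals: "Other facilities are encouraged to follow this protocol, however, the ultimate decision for blood transfusion will be at the discretion of the treating physician". Transfusions during surgery also count towards the outcome, since "both intraoperative and postoperative incidents of blood transfusion will be monitored to calculate transfusion rates", but no trigger for them is given at any site.

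Section II.G states: "This will be a multi-institutional study with the University of Kansas Medical Center being the coordinating site". It names seven interested outside institutions and adds that there are others; it gives neither a final number of sites nor expected enrolment by site. Section II.I.2, answering a template question on whether procedures are the same everywhere, replies "Identical across sites".

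Randomization is central, through REDCap. Section II.C says "Treatment assignments will be stratified by type of resection"; section II.B says "Treatment assignments will be stratified by type of resection location". Site is not mentioned as a stratifier. Section V.A lists transfusion requirements, 24-hour drain output, the hemoglobin balance result "and changes in hemoglobin and hematocrit will be compared using pairwise Student T-test analysis". Chi-squared tests are planned for categorical patient factors. No comparison carries a site term.

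**The concern.** Transfusion rate is hypothesis 2 and a named secondary outcome. By making the trigger firm at one hospital and advisory elsewhere, the plan itself identifies a reason why transfusion rates might vary by site. It then neither balances site between arms nor allows for it in the analysis. If the arms happen to differ in their mix of hospitals, part of an observed difference in transfusion could come from that mix. Even with a balanced mix, between-site variation left in the error term costs power. Differences in surgeon and technique between sites could act on blood loss and drain output in the same way. The bone stratum, with 20 patients per arm, is the most exposed.

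**Working it through.** **Inputs from the documents.** 20 per arm (bone) and 50 per arm (soft tissue), from II.B and II.C. Section II.C attaches a power of 0.9 to these numbers but gives no endpoint, alpha, effect size or standard deviation, so they cannot be reproduced. The point disputes no stated figure.

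**Assumptions.** The documents give no site shares and no transfusion rates. I use a coordinating-site share q of 30% to 50%, and transfusion rates at the two kinds of site of 20% and 60% (strong contrast) or 30% and 50% (milder). Both pairs average 40% when q = 0.5.

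**1. How often does the site mix differ between arms?** Treat the number of coordinating-site patients in each arm as an independent binomial (n, q). The probability that the shares differ by 20 points or more is:

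| | q = 0.3 | q = 0.5 |
|---|---|---|
| 20 per arm | 0.226 | 0.268 |
| 50 per arm | 0.038 | 0.057 |

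If the coordinating site enrolled 80% to 90% of patients, these fall to 16% to 6% (bone) and 1.7% to 0.2% (soft tissue).

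**2. What does that do to the transfusion difference?** With a gap g between the two rates, the standard deviation due to site mix alone is g × √(2q(1−q)/n). At q = 0.5:

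- 20%/60%, 20 per arm: 0.40 × √(0.5/20) = 0.063; 50 per arm: 0.40 × √(0.5/50) = 0.040.
- 30%/50%, 20 per arm: 0.20 × √(0.5/20) = 0.032; 50 per arm: 0.20 × √(0.5/50) = 0.020.

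In simulation, site mix alone produced a difference of at least 5 points in about 44% (20 per arm) and 20% (50 per arm) of trials at 20%/60%, and in about 16% and 1% at 30%/50%. Eight equal sites spread from 20% to 60% gave standard deviations of 4.1 and 2.6 points, and at least 5 points in about 22% and 5%.

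**3. Set against ordinary sampling error.** At an overall rate of 40%, the standard error of the arm difference is √(2 × 0.4 × 0.6/20) = 0.155 and √(2 × 0.4 × 0.6/50) = 0.098. Site mix is part of this, not an addition to it: 0.063²/0.155² is about 1/6 of the variance at 20%/60%, and 0.032²/0.155² about 4% at 30%/50%. As one worked case, a 20-point imbalance with a 30-point gap shifts the difference by 0.20 × 0.30 = 6 points, and 0.06/0.155 = 0.39 standard errors.

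**4. Validity and power.** With no treatment effect and randomization ignoring site, the simulated mean difference was about 0 and the type I error of an unadjusted two-proportion test about 5% in every scenario. Power for a true 15-point reduction at 50 per arm:

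| Site rates | Unadjusted | CMH stratified by site |
|---|---|---|
| 20%/60% | about 35% | about 41% |
| 30%/50% | about 36% | about 37% |

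Balancing the randomization by site as well, at 20%/60%, brought the CMH figure to about 43%. At 20 per arm, the change from unadjusted to CMH was 17% to 19% at 20%/60%, and nil (17% for both) at 30%/50%.

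**The case against.** The strongest reply is that this is noise, which an ordinary test already allows for. That stands: a reader might infer that unbalanced sites bias the transfusion comparison, but central randomization rules that out, and step 4 shows no inflation of type I error.

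Second, the size rests on assumed site shares and rates. That also stands. Outside institutions have so far only expressed interest and are waiting for ethics approval, so the coordinating site could dominate and the issue shrink.

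Third, a reader might infer that the outcome arises under two distinct transfusion regimes. The text does not go so far. It recommends one rule and leaves the final decision elsewhere to the physician; nothing shows that other sites will depart from it. Intraoperative transfusion has no stated trigger even at the coordinating site.

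Fourth, a reader might call II.B and II.I.2 a flat contradiction. The template question concerns study activities, and transfusion can be read as routine care. But transfusion generates a named outcome, so clarification is warranted. Two further inferences are weak: that site will go unrecorded (the list of recorded patient factors in II.B is open-ended), and that the two stratification phrases imply different lists (the four groups in II.B show a bone versus soft-tissue split).

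Finally, surgeons are unblinded and transfusion can be discretionary, so decisions could differ by arm. That is a separate concern, and nothing proposed here addresses it.

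**Conclusion.** The point holds as a minor one. The plan foresees that transfusion practice may vary by site and leaves that variation in its arm comparisons. The consequence is lost precision and possible distortion of a single realised result, not systematic error. Under assumed contrasts of 20 to 40 points between two equally common kinds of site, site mix contributes a standard deviation of about 3 to 6 points in the bone stratum and 2 to 4 points in the soft-tissue stratum. Adjustment gains about 1 to 6 points of power at 50 per arm. If sites hardly differ, or one site enrols nearly everyone, there is little to gain. The inconsistency between II.B and II.I.2 is a matter of wording.

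**What to change.** - **Record site** for every patient.
- **Section V.A (and II.C to match):** within each resection stratum, compare transfusion rates with a Cochran-Mantel-Haenszel test stratified by coordinating versus other sites. Compare blood loss and drain output with a linear model containing treatment and the same two-level factor. Two levels are preferable to individual sites, which could be very sparse among 40 bone patients. Pooling the outside sites does leave differences among them unadjusted.
- **Randomization (optional):** if it has not begun, the same factor can be added to the REDCap stratification, giving four strata. With unblinded surgeons this choice is more debatable. If it is made, the analysis must include the factor: with site-balanced allocation and 20%/60% rates, the unadjusted test was conservative, with type I error of about 3% to 4%.
- **Sections II.B and II.I.2:** reconcile whether transfusion practice is meant to be identical across sites. No view is taken here on what the rule should be.

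The cost is one recorded field, one model term and some SAP wording, with little power lost if sites do not differ. The analysis change remains possible after enrolment has started, but should be fixed before outcome data are examined by arm.

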5. Timeline: Patients will be seen at routine post-operative visits at 2-3 weeks, 6 weeks, and 3 months where clinical examination and history taking will take place.

F. Risk/benefit assessment:

1. Physical risk: The primary concern with the use of TXA is the theoretical risk of developing a deep venous thrombosis. The patients will be monitored clinically for signs and symptoms of DVT while they are admitted to the hospital as well as at routine postoperative visits.
2. Psychological risk: We do not anticipate any psychologic risk to participants in this study.
3. Social risk: We do not anticipate any social risk in this study.
4. Economic risk: There will be no cost to subjects during this study, neither will there be any remuneration.
5. Potential benefit of participating in the study
 - a. to the individual subject and/or parent if any: None
 - b. to the population from which the subject is drawn: TXA in this patient population is sporadic and varies widely from surgeon to surgeon. Providing a definitive answer regarding the safety and efficacy of TXA in this patient population would both unify the musculoskeletal oncology field in their use or abandonment of TXA,

and potentially improve oncologic patient care in a similar fashion than that seen with the use of TXA in arthroplasty.

- c. to science, society, and humanity in general: A definitive answer regarding the safety and efficacy of TXA in this patient population would both unify the musculoskeletal oncology field in their use or abandonment of TXA

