2. Primary responsibility for the following activities, for example:
 - a. Determining eligibility: [name] MD, [name] MD, [name], MD
 - b. Obtaining informed consent: [name] MD, [name] MD, [name] MD
 - c. Providing on-going information to the study sponsor and the IRB: [name] MD, [name] MD, [name]
 - d. Maintaining participant's research records: [name] MD, [name] MD, [name]
 - e. Completing physical examination: [name] MD, [name] MD, [name] MD
 - f. Taking vital signs, height, weight: Clinical support staff for participating surgeons
 - g. Drawing / collecting laboratory specimens: Clinical support staff for participating surgeons
 - h. Performing / conducting tests, procedures, interventions, questionnaires: [name] MD, [name] MD, [name] MD

- i. Completing study data forms: [name] MD, [name] MD, [name] MD, [name] MD
- j. Managing study database: [name] MD, [name] MD, [name]

L. Assessment of Subject Safety and Development of a Data and Safety Monitoring Plan

1. Please note that any study proposal with more than minimal risk must include a data and safety monitoring plan. Elements of the plan include:
 - a. Persons/groups who will review the data (study team; independent safety monitor, data monitoring committee or formal DSMB) - Study team
 - i. An independent safety monitor will be used. [name], MD is an orthopaedic surgeon familiar with the use of TXA and uninvolved with the study in any other capacity.
 - b. Data/events that will be reviewed - Adverse events/complications arising in the participating patients.
 - c. Frequency of review: Review will occur every 4 months routinely. Additionally, a review will be conducted if 5 separate adverse events are reported prior to the scheduled bi-annual review.
 - d. Types of analyses to be performed – we will analyze the rate of complications (infections, PE, DVT) between the groups to make sure that we aren't getting statistically significant differences between groups
 - e. Safety-related triggers that would cause the PI to stop or alter the study – If our analysis of complications reveals a statistically significant difference between groups, we will place the study on hold until an appropriate remedy can be reached. We will consult with the IRB before resuming the study. If no remedy can be determined the study will be permanently held

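### DVT and PE are sought on symptoms by clinicians who probably know the arm, and testing is not recorded by arm, so the safety comparison cannot separate events from looking

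*Combined protocol and SAP*

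**What the plan says.** **How events are found.** Section II.B has patients followed clinically each day in hospital and at later visits for symptoms of DVT or embolism, and adds that "appropriate diagnostic screening with venous Doppler will be utilized if symptoms are present". Section II.F.1 (Physical risk) names DVT as the main concern with TXA and says "The patients will be monitored clinically for signs and symptoms of DVT while they are admitted to the hospital", and again at the postoperative visits. Section II.E.5 sets those visits: "Patients will be seen at routine post-operative visits at 2-3 weeks, 6 weeks, and 3 months". Section II.E.3 says that no test is done for research alone.

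**Who knows the arm.** Sections II.B and II.C both state that "investigators/surgeons are not blinded" and that "Patients will be blinded to treatment allocation". The reason given in II.C is: "Since we are gathering entirely objective data the treating surgeon does not need to be blinded".

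**What the counts are used for.** Section II.L.1.d says "we will analyze the rate of complications (infections, PE, DVT) between the groups". Under II.L.1.e a statistically significant difference puts the study on hold pending IRB consultation. The withdrawal and termination paragraph of II.D also suspends the study if complications are out of proportion in one group. An independent safety monitor is named in II.L.1.a.

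**What is not described.** The plan gives no criteria for ordering a test, no definition of a confirmed DVT or PE, no masked confirmation of events, and no record of tests done by arm.

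**The concern.** The argument in II.C that objective data make surgeon blinding unnecessary may serve for hemoglobin. It does not reach this outcome. A Doppler report is fairly objective, but deciding that a patient has symptoms after a large lower-extremity resection, and that they warrant a test, is a judgement. The clinicians likely to make it know the arm, and their own protocol tells them that DVT is the main TXA concern.

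The direction of any bias is not fixed. Heightened suspicion could bring more testing on TXA and a spurious excess. Reassurance from the arthroplasty safety literature cited in I.B could bring less testing and hide a real excess. Section I.B also cites less postoperative pain and swelling with TXA in arthroplasty, which, if it carries over, could reduce the triggers for testing in that arm.

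Two things are at stake: whether a hold or suspension reflects harm or looking, and whether the final safety statement can be interpreted. The protocol says the study should settle the safety of TXA in this population. If numbers tested are not recorded as the trial runs, they may not be recoverable afterwards.

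**Working it through.** The plan states no expected DVT or PE rate for this population and no sample size for safety, so there is no figure of its own to reproduce. The check asks how far unequal detection alone can move the comparison in II.L.1.

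**Inputs from the documents**
- Patients per arm: 20 (bone) + 50 (soft tissue) = 70 (II.C).
- Trigger: a statistically significant difference between groups (II.L.1.e).
- The only VTE rate given is 2%, for recurrence in arthroplasty patients with prior VTE (I.B), a different population.

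**Assumptions**
- Strata pooled; two-sided 0.05; a single look; chi-squared without continuity correction, with Fisher's exact test alongside. The plan does not specify the level or the test for this comparison.
- True event rates of 2% to 20%.
- Detection of 90% in one arm and 45% in the other, compared with 90% in both.

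**Step 1. How few events matter.** With 70 per arm, 4 v 0 is significant by chi-squared (p = 0.042) and so is 7 v 1 (p = 0.029). Fisher needs 6 v 0 (p = 0.028) or 8 v 1 (p = 0.033).

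**Step 2. No true difference, unequal detection.** With true rate π and detection fractions d₁ and d₂, the observed counts are A ~ Bin(70, πd₁) and B ~ Bin(70, πd₂). The chance of a significant look is the sum, over all pairs (a, b) with p(a, b) < 0.05, of P(A = a) × P(B = b). At π = 10% the expected counts are 70 × 0.10 × 0.90 = 6.3 and 70 × 0.10 × 0.45 = 3.15, an apparent risk ratio of 0.90/0.45 = 2 with no true effect.

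| True rate, both arms | Expected counts, 90% v 45% | Chi-squared: equal 90% | Chi-squared: 90% v 45% | Fisher: equal 90% | Fisher: 90% v 45% |
|---|---|---|---|---|---|
| 2% | 1.26 v 0.63 | 2.1% | 2.1% | 0.1% | 0.1% |
| 5% | 3.15 v 1.57 | 4.7% | 9.8% | 1.2% | 2.4% |
| 10% | 6.3 v 3.15 | 5.2% | 18% | 2.4% | 9.7% |
| 20% | 12.6 v 6.3 | 5.0% | 34% | 3.1% | 27% |

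**Step 3. Lower detection, same twofold ratio.** With 60% v 30% detection at a true rate of 10%, the observed rates are 0.10 × 0.60 = 6% and 0.10 × 0.30 = 3%. The chance of a significant look is 12.5% by chi-squared (Fisher 4.7%), against 4.1% (Fisher 0.5%) with both arms observed at 3%. At a true rate of 2%, the same fractions give only 0.7% by chi-squared.

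**Step 4. A real excess hidden.** Take a true 15% on TXA v 5% in control. With 90% detection in both arms the observed rates are 13.5% v 4.5%, and the chance of a significant look is 48% (Fisher 35%). With 45% detection on TXA and 90% in control they are 6.75% v 4.5%, and the chance falls to 8.5% (Fisher 3.4%).

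The repeated reviews in II.L.1.c are not modelled.

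**The case against.** The case on the other side has several parts.

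- **Symptomatic VTE is a legitimate endpoint.** It is a sensible clinical outcome and is not a primary or secondary outcome here. A hold is provisional and goes through the IRB, and an independent monitor reviews events. All true. But the monitor sees only what has already been detected and reported, so review does not correct unequal testing.
- **Patients are blinded.** This stands as partial protection for symptom reporting. It does not cover how symptoms are elicited or who is sent for a test.
- **The protocol does not say who orders the Doppler.** Correct. A reader might infer that events are found only when the unblinded surgeon acts. That is likely from the design, but it is an inference.
- **A false hold is not a given.** A reader might infer that modestly unequal testing will stop the trial. It need not: 4 v 2 events of 70 gives p = 0.40 (Fisher 0.68), and at a 2% true rate there is no inflation. Nor do the documents show that testing will be heavier on TXA.
- **The sections on PE do not conflict.** A reader might see a contradiction because II.B names only venous Doppler, II.F.1 mentions only DVT, and II.L.1.d counts PE. They differ in completeness. Section II.B covers embolism, and naming one test does not exclude others. What is missing is a statement of what counts as a PE.
- **DVT and PE are not the whole safety comparison.** Infections are counted too.

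**Conclusion.** The concern holds as a weakness in ascertainment. Testing is triggered by symptoms, the clinicians likely to judge those symptoms are unblinded, and numbers tested are not recorded by arm. A between-arm difference in DVT or PE, or the lack of one, therefore cannot be separated from a difference in testing.

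The size depends on assumed rates and detection fractions. Twofold unequal detection has no effect on the false-signal rate at 2%, roughly doubles it at 5%, and raises it to between 18% and 34% at true rates of 10% to 20% by chi-squared; Fisher gives lower figures. In the other direction, the assumed threefold true excess could go from about an even chance of being seen to under one in ten. The suspension rule in II.D sets no statistical threshold, so its exposure cannot be quantified.

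The documents do not show that bias will occur or which way it would run. The plan should be changed because the remedy is cheap and the missing information may not be recoverable later.

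**What to change.** 1. Use the same short DVT/PE symptom checklist in both arms, daily in hospital and at the existing 2-3 week, 6 week and 3 month visits.
2. Log every imaging study known to the site that was done for suspected DVT or PE, with its reason and result, negatives included.
3. Report the number of patients tested in each arm beside the number of events, at each safety review and in the final report.
4. State in II.L.1.d what record counts as a confirmed DVT and a confirmed PE.
5. Have the existing independent monitor confirm each event from an imaging report with the arm redacted, before any unmasked discussion with the investigator and treating surgeon under II.L.3.

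Items 1 to 3 address unequal testing: the checklist makes elicitation more uniform, and the tested counts make any remaining imbalance visible. Unblinded staff may still complete the checklist, so it reduces the problem without removing it. Items 4 and 5 make classification consistent but cannot correct for patients who were never tested.

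No additional test and no change in clinical management is proposed. The cost is modest extra data entry at sites and redaction of a few reports.
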